- 1 This study (1363.7) will only start once healthy volunteers have been safely administered 100 and 400 µg b.i.d. of BI 443651 for 7days in a separate ongoing study (1363.2) i.e. no stopping criteria have been triggered in 1363.2.
- 2 Only mild, controlled, stable asthma subjects with well-maintained lung function will be included in the study i.e. subjects on prn SABA or low dose inhaled corticosteroid with an $FEV_1 \geq 70\%$ and no recent respiratory tract infection or exacerbation.
- 3 The study will be split into two parts ([see Section 3.1](#)) with an initial pilot (Part 1) to assess for gross adverse effects of BI 443651 on bronchoconstriction after MCh challenge. In Part 1, subjects will receive BI 443651 in a dose ordered fashion with either placebo **or** the lowest dose first followed by the higher doses and placebo (if not taken first). Individual subjects will not be dosed further if individual stopping criteria (including pulmonary function criteria) are triggered. Stopping criteria are described in detail in [Section 3.3.4](#).

The second part of the study (not necessarily dose ordered) will only proceed if no subjects triggered the first three discontinuation criteria following administration of BI 443651 during Part 1.

- 4 The subjects will be closely monitored throughout the treatment period with frequent evaluation of pulmonary function following MCh challenge. Subjects may only be discharged from clinic after medical assessment has been conducted. The subject's FEV_1 must have returned to $\geq 90\%$ of the first set of spirometry measurements performed that day before the subject can be discharged from the clinic. Rescue medication will be provided as required.
- 5 Safety laboratory testing will be performed during the study with a focus on electrolytes ([see Flow Chart](#)). The study will be stopped if, during Part 1 (pilot) at least 2 subjects in the current cohort or treatment period on active drug showed serum potassium levels $\geq 5.5\text{mmol/L}$ in non-haemolysed blood (confirmed by repeat). In Part 2 (main study), the study would be stopped if 4 subjects on active drug (independent of dose level) showed serum potassium levels $\geq 5.5\text{mmol/L}$ in non-haemolysed blood (confirmed by repeat).

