3. DESCRIPTION OF DESIGN AND TRIAL POPULATION

3.1 OVERALL TRIAL DESIGN AND PLAN

This multiple dose, randomised, placebo controlled, trial will be conducted in two parts. The first part (pilot study) will be a single-blind four-way crossover with dose ordered sequences. The second part (main study) will be a double-blind four-way crossover, conducted according to a William's design. In both parts of the study, BI 443651 or placebo equivalent will be administered three consecutive times, 12 hours apart, per dose level. All subjects will receive placebo, 100, 400 and 1200 µg BI 443651 (in Part 1, the dose groups may be altered in case evolving data suggests a change in dosage is required (see below)). Each period will be separated by a washout period of at least 14 days (and not more than 28 days). Two administrations of BI 443651 will be delivered on Day 1 (morning and evening) and a single administration Day 2 (morning). One hour after dosing on Day 2, MCh challenge will be performed. A methacholine challenge will be conducted on Day -2 to Day -1 for each treatment period, (with the Day -2 to Day -1 challenge providing the baseline for each treatment period) at the same time of the day.

The two parts of the study will be conducted as follows:

Part 1: 4 subjects will be included in the first pilot part of the study each being administered three active doses of BI 443651 and placebo, with the active doses investigated being in ascending order of dose strength. Placebo administered given in a single-blinded manner in any order relative to the active treatment as per Table 3.1:1.

Table 3.1:1 Sequences for pilot part of the study

Treatment Period 1	Treatment Period 2	Treatment Period 3	Treatment Period 4
Placebo	100 µg	400 µg	1200 µg
100 µg	Placebo	400 µg	1200 µg
100 µg	400 µg	Placebo	1200 µg
100 µg	400 µg	1200 µg	Placebo

Part 2: 32 subjects will participate in the trial with each subject being administered three active dose levels of BI 443651 and placebo. This part of the study will be fully randomised, double blind. The decision to proceed to Part 2 will be based upon the safety and tolerability data of Part 1. Part 2 will only be conducted if, in the opinion of the investigator, no safety concerns arose in Part 1 and if none of the pre-specified trial-specific stopping criteria were met ([see Section 3.3.4.2](#)).

Table 3.1:2

Sequences for main part of the study

Treatment Period 1	Treatment Period 2	Treatment Period 3	Treatment Period 4

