Placebo	100 µg	400 µg	1200 µg
100 µg	Placebo	1200 µg	400 µg
400 µg	1200 µg	Placebo	100 µg
1200 µg	400 µg	100 µg	Placebo

The first pilot part of the study will not be started until data from an ongoing multiple rising dose study (1363.2) in healthy volunteers is available from the first two dose groups (100 and 400 µg b.i.d. BI 443651). Only if BI 443651 has been safely administered in study 1363.2 and no stopping criteria have been met, will this study (1363.7) be started.

In Part 1, dose groups will be investigated consecutively in ascending order of doses with a dose escalation review between each treatment period. Data from each treatment level will be reviewed prior to progression to the next treatment level. Only if the previous dose of BI 443651 is safe and well tolerated, without meeting any stopping criteria in subjects administered BI 443651 ([see Section 3.3.4.1](#)), will the subsequent dose be administered ([Table 3.1:1](#)).

In addition a documented Safety Review by the Coordinating Investigator (or an authorised deputy) and appropriate personnel from the Sponsor must take place prior to initiation of Part 2 of the study. Only if BI 443651 is safe and well tolerated in all subjects in the pilot part without the specified number of subjects meeting any individual stopping criteria (see Section 3.3.4.1), will the transition to Part 2 occur.

An unscheduled safety review meeting can be requested anytime for any reasonable cause by the Principal Investigator (or an authorised deputy) or the sponsor of the study, e.g. because of any unforeseen adverse events, etc. Dose escalation or transition to Part 2 will only be permitted if no safety concerns exist in the opinion of the Principal Investigator (or an authorised deputy) and the Trial Clinical Monitor (or an authorised deputy). The minimum data set for review consists of the following data:

- Results from spirometry in all subjects included in the initial pilot part of the study
- AEs in all subjects including in the initial pilot part of the study, up to at least 48h post dosing (including clinically relevant findings from ancillary safety testing listed below) (Note: AEs may be ongoing at the time of Safety Reviews and AE information may be subject to change prior to Database Lock)
- Check of criteria for stopping subject treatment as per Section 3.3.4.1

Proprietary confidential information © 2017 Boehringer Ingelheim International GmbH or one or more of its affiliated companies

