3.3.4.2 Discontinuation of the trial by the sponsor

Boehringer Ingelheim reserves the right to discontinue the trial overall or at a particular trial site at any time for the following reasons:

1	Failure to meet expected enrolment goals overall or at a particular trial site
2	Emergence of any efficacy/safety information invalidating the earlier positive benefit-risk assessment that could significantly affect the continuation of the trial.
3	Violation of GCP, the CTP or the contract disturbing the appropriate conduct of the trial
4	New toxicological findings or serious adverse events invalidate the earlier positive benefit-risk assessment. More specifically, the trial will be terminated if two subjects have, at least, possibly related SAE or in case of the occurrence of three, at least, possibly related severe AEs. No further dosing, dose escalation or inclusion of any further

Proprietary confidential information © 2017 Boehringer Ingelheim International GmbH or one or more of its affiliated companies

	subjects (independent of dose level) will occur without approval of a substantial amendment.
5	
Part 1 (pilot study): At least 2 subjects* in the current cohort or treatment period on active drug showed serum potassium levels $\geq 5.5\text{mmol/L}$ in non-haemolysed blood (confirmed by repeat).
 
Part 2 (main study): At least 4 subjects* on active drug (independent of dose level) showed serum potassium levels $\geq 5.5\text{mmol/L}$ in non-haemolysed blood (confirmed by repeat).
 
* These are proposed thresholds for potential trial discontinuation however any and all individual occurrences of serum potassium levels $\geq 5.5\text{mmol/L}$ in non-haemolysed blood will be reviewed by the PI and sponsor medical team.

6	
At least 2 subjects independent of dose level on active drug showed relevant individual QT prolongation, i.e. a QTcF increase of greater 60 ms from baseline in connection with absolute QT or QTcF greater than 500 ms, which has been confirmed by a repeat ECG recording*
 
*These are proposed thresholds for potential trial discontinuation however any and all individual occurrences of QT prolongations will be reviewed by the PI and sponsor medical team

The Investigator / trial site will be reimbursed for reasonable expenses incurred in case of trial termination (except in case of the third reason).

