4.1.5 Blinding and procedures for unblinding

4.1.5.1 Blinding

In the pilot part of the study (Part 1), site staff dosing the subjects will be unblinded. Unblinded site staff will not conduct any study assessments.

The main part of the study (Part 2) will be double-blind and subjects, investigators and everyone involved in trial conduct or analysis or with any other interest in this trial will remain blinded with regard to the randomised treatment assignments until after database lock.

The randomisation code will be kept secret by Clinical Trial Support up to database lock.

The randomisation codes will be provided to bioanalytics prior to the last subject out date to allow for the appropriate analyses of pharmacokinetic (PK) samples taken from different dose strengths. Bioanalytics will not disclose the randomisation code or the results of their measurements until the trial is officially unblinded.

The trial will only be unblinded after locking of the database.

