7.4 PRIMARY ENDPOINT

CTP: *The primary endpoint absolute change from baseline in maximum reduction in FEV1 (refer to Section 5.1.1 of the CTP) is defined as the difference between the maximum reduction in FEV1 obtained during the treatment challenge and during the baseline challenge.*

The primary endpoint will be analyzed based on the MCS.

Descriptive statistics and boxplots of the primary endpoint by treatment (and by trial part) will be provided.

As main analysis, the following model will be applied to the main part of the trial (part II).

Statistical model

CTP: [...] this primary endpoint will be analysed using a mixed effects model based on the MCS:

$$y_{imj} = \mu + \pi_m + \tau_j + \gamma b_{im} + \gamma' b_i' + s_i + e_{imj},$$

where $i = \text{subject } 1, \dots, N$, $m = \text{period } 1, \dots, 4$, $j = \text{treatment } 1, \dots, 4$

y_{imj}	CfB in maximum FEV₁ reduction for the i^{th} subject and the m^{th} period, receiving randomised treatment j
μ	overall intercept,
π_m	m^{th} period effect,
τ_j	j^{th} treatment effect,
b_{im}	baseline value for subject i in period m (period baseline),
γ	associated covariate effect of period baseline,
b'_i	the subject baseline value (mean of period baselines) for subject i,
γ'	associated covariate effect of subject baseline,
s_i	the random effect of subject i,
e_{imj}	the random error associated with subject i who received treatment j in period m.

The treatment comparisons will be the contrast (difference) between active dose and placebo at the endpoint visit. Adjusted means (Least Squares Means) as well as 2-sided 90% CIs will be provided.

For the random ‘subject’ effect in the above model a Variance Components (VC) covariance structure will be used; in case of convergence problems refer to Additional Section [9.1](#). The SAS procedure MIXED will be used involving the restricted maximum likelihood estimation and the Kenward-Roger approximation for denominator degrees of freedom. This approach is described in Kenward and Roger ([11](#)).

Programming details are provided in Section [9.2.1](#).

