7.8 SAFETY ANALYSIS

All safety analyses of further safety parameters of interest will be performed on the treated set (and will be presented for both trial parts combined).

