7.8.2 Laboratory data

The analyses of laboratory data will be descriptive in nature and will be based on BI standards (6). If possible, analyses will be based on normalized values. If multiple reference ranges apply for one parameter (e.g. due to different age groups), analyses will be based on normalised values, which means transforming to a standard unit and a standard reference range.

Laboratory data will be analysed both quantitatively as well as qualitatively. The latter will be done by comparing laboratory data to their reference ranges. Values outside the reference range as well as values defined as clinically relevant will be highlighted in the listings.

Treatment groups will be compared based on descriptive statistics of laboratory values over time and by analysing differences from baseline. Additionally, frequency tables of changes between baseline and last values on treatment with respect to the reference ranges as well as frequencies and percentages of subjects with abnormal values or clinically relevant abnormal values will be presented.

Clinically relevant findings in laboratory data will be reported as AEs and will be analysed as part of AE analysis.

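### SAP 7.8 gives the AE, laboratory and vital-sign tables only for Parts 1 and 2 pooled; once Part 2 has run, this slightly favours active drug on three selected events and ties dose to period

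*SAP*

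**What the plan says.** SAP 7.8 states that analyses of the further safety parameters will be "performed on the treated set (and will be presented for both trial parts combined"). SAP 7.8.1 to 7.8.3 then describe the AE, laboratory and vital-sign summaries by treatment, with no split by part. For laboratory data, for example, "frequencies and percentages of subjects with abnormal values or clinically relevant abnormal values will be presented".

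The FEV1 endpoints are handled differently. SAP 7.4 says "Descriptive statistics and boxplots of the primary endpoint by treatment (and by trial part) will be provided", and the model is fitted to Part 2 only. SAP 7.5 does the same for the secondary endpoints.

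The move from Part 1 to Part 2 is worded in three ways:

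- Protocol 2.3, safety measure 3: Part 2 "will only proceed if no subjects triggered the first three discontinuation criteria following administration of BI 443651 during Part 1". The first three criteria in Protocol 3.3.4.1 are an FEV1 fall of 45% or more after methacholine, confirmed potassium of 5.5 mmol/L or more, and QTcF prolongation.
- Protocol 3.1, on Part 2: it is run if the investigator sees no safety concerns in Part 1 and "if none of the pre-specified trial-specific stopping criteria were met", with a pointer to 3.3.4.2. There the Part 1 potassium threshold is "At least 2 subjects* in the current cohort or treatment period on active drug".
- Protocol 3.1, on the safety review: transition occurs "without the specified number of subjects meeting any individual stopping criteria", and no number is given at that point.

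**The concern.** Protocol 2.2 makes safety and tolerability the primary objective, and active dose against placebo is the comparison a reader will take from the safety tables. Two features of Part 1 make pooling less than neutral for that comparison.

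First, selection. On the Protocol 2.3 wording, a table containing Part 2 data can exist only if the Part 1 active periods had no criteria a–c event. That sentence does not cover the Part 1 placebo periods. Pooling then adds active periods with a built-in zero for those events and placebo periods without one.

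Second, period. The Part 1 sequences in Table 3.1:1 give the active doses in ascending order, so dose and period go together. Part 2 is balanced over periods, and the safety tables are descriptive with no period adjustment. Pooling gives up some of the balance that the Part 2 design provides.

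**Working it through.** **Plan's own figure.** At least 36 subjects: 4 (Part 1) + 32 (Part 2) = 36, which agrees with the Protocol synopsis. Each subject takes placebo and three active doses. Each treatment therefore has 4 + 32 periods, and the active doses together have 12 + 96 = 108.

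**Selection.** Let p be the chance of a criteria a–c event in a period. The documents give no value. I assume p from 0.01 to 0.10, equal on active and placebo and independent between periods. I also assume 4 + 32 completers and unchanged doses.

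- Protocol 2.3 wording, given that Part 2 is run: the expected rate per active dose is (4 × 0 + 32p)/36 = 0.889p, and the placebo rate is p. The factor 32/36 does not depend on p. The difference, p/9, equals 4p subjects in a column of 36.
- If one event in the 12 active periods may pass: the expected number of Part 1 active events is e = 12p(1−p)^11 / [(1−p)^12 + 12p(1−p)^11], and the pooled active rate is (e + 96p)/108.
- Chance that the Protocol 2.3 condition is met: (1−p)^12.

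| p | Condition met | Pooled active rate, Protocol 2.3 | Difference (points) | Subjects per dose column | Ratio to p if one event may pass |
|---|---|---|---|---|---|
| 0.01 | 0.886 | 0.0089 | −0.11 | 0.04 | 0.989 |
| 0.02 | 0.785 | 0.0178 | −0.22 | 0.08 | 0.980 |
| 0.05 | 0.540 | 0.0444 | −0.56 | 0.20 | 0.961 |
| 0.10 | 0.282 | 0.0889 | −1.11 | 0.40 | 0.942 |

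Part 2 alone has expected rate p in every column, so there the distortion is zero.

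**Without conditioning on Part 2.** Average the reported rate over all outcomes, including trials that stop after Part 1, and suppose all 12 active periods are given. The expected active rate is (1−p)^12 × 32p/36 + p, which is 0.018, 0.034, 0.074 and 0.125 for the four values of p. That is above p. The downward shift exists only once Part 2 has run, which is also the only case with a two-part table.

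**Period.** Counts from Tables 3.1:1 and 3.1:2, with 8 subjects per Part 2 sequence:

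| Treatment | Part 1, Periods 1/2/3/4 | Part 2 | Combined |
|---|---|---|---|
| Placebo | 1/1/1/1 | 8/8/8/8 | 9/9/9/9 |
| 100 µg | 3/1/0/0 | 8/8/8/8 | 11/9/8/8 |
| 400 µg | 0/2/2/0 | 8/8/8/8 | 8/10/10/8 |
| 1200 µg | 0/0/1/3 | 8/8/8/8 | 8/8/9/11 |

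The mean period in the combined data is (11 + 18 + 24 + 32)/36 = 2.36 for 100 µg and (8 + 16 + 27 + 44)/36 = 2.64 for 1200 µg. It is 2.50 for placebo and 400 µg. In Part 2 alone it is 2.50 for all four. This imbalance does not depend on which transition wording applies.

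**The case against.** Much of the case for leaving the plan as it is stands.

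- A reader might infer that Part 1 active periods enter the tables only if they are event-free. They do not. The treated set in SAP 6.3 keeps every randomised and treated subject, and if the trial stops after Part 1 the events are still reported. The selection acts on whether Part 2 exists.
- A reader might infer that harm on active drug is understated in general. Only criteria a–c are directly conditioned. Other AEs and vital signs could be touched only indirectly. The FEV1 fall is covered by the primary endpoint, shown by part. SAP 7.8.4 plans no QTc table, so QTcF reaches the tables only as an AE.
- For potassium the built-in zero is approximate. Protocol 5.3.3 bases dosing decisions on local results, which are not entered in the database, so the tables use central values and reference ranges.
- Only one of the three transition wordings gives the full 11%. Protocol 3.1 also requires no safety concerns in Part 1 overall, so placebo periods are not wholly outside every condition.
- A reader might point to the end-of-trial visit, which follows 1200 µg in 11 subjects, placebo in 9, and 100 µg and 400 µg in 8 each. Whether those data count as on-treatment depends on the residual effect period, whose length is not visible in the public text. No distortion can be shown.
- A reader might also infer biased assessment from "In the pilot part of the study (Part 1), site staff dosing the subjects will be unblinded". The next sentence of that section bars those staff from study assessments, so this is not established.
- The analyses are descriptive, a four-subject table says little by itself, and SAP 7 lists all individual values. These points limit the consequence. They do not supply an unselected, period-balanced summary, because a listing is not a substitute for one.

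**Conclusion.** The point holds as a small, one-directional weakness in presentation. Given that Part 2 is run under the Protocol 2.3 wording, the pooled active rate of criteria a–c events is at most 11% (relative) below the Part 2 rate. If one event may pass, the shortfall is about 1 to 6%. For assumed rates up to 0.10 it stays below half a subject per dose column. It is largest in absolute terms where the condition is least likely to be met: 0.282 at p = 0.10.

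Pooling also introduces a mild dose-by-period imbalance that Part 2 alone does not have. The documents do not support a wider claim that the safety tables hide harm on active drug. The rates p are assumptions. The factor 32/36 rests only on the planned subject numbers, unchanged Part 1 doses and the Protocol 2.3 wording.

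**What to change.** In SAP 7.8, state that the AE, laboratory and vital-sign tables will be given for Part 2 alone and for Part 1 alone, in addition to the combined tables, and that the descriptive comparison of active doses with placebo will be read from Part 2. This matches how SAP 7.4 and 7.5 already treat the FEV1 endpoints, and the combined tables remain available.

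The cost is one further run of existing table programs and 32 instead of 36 subjects per treatment in that comparison. Standard errors rise by a factor of about √(36/32) = 1.06.

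Separately, the three wordings of the condition for starting Part 2 (Protocol 2.3 and the two statements in 3.1, one of which points to 3.3.4.2) should be reconciled, so that it is clear what selection the Part 1 data have undergone. Which rule should apply is for the sponsor and the investigator to decide.

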7.8.1 Adverse events

AEs will be coded with the most recent version of MedDRA.

The analyses of AEs will be descriptive in nature. All analyses of AEs will be based on the number of subjects with AEs and not on the number of AEs.

For analysis, multiple AE occurrence data on the electronic case report form (eCRF) will be collapsed into one event provided that all of the following applies:

- All AE attributes are identical (lower level term, intensity, action taken, therapy required, seriousness, reason for seriousness, relationship, outcome, AE of special interest (AESI))
- The occurrences were time-overlapping or time-adjacent (time-adjacency of two occurrences is given if the second occurrence started at most 1 hour after the first occurrence ended)

For further details on summarization of AE data, please refer to 'Handling and summarization of adverse event data for clinical trial reports and integrated summaries' ([4](#)) and "Handling of missing and incomplete AE dates" ([3](#)).

The analysis of AEs will be based on the concept of treatment emergent AEs, i.e. all AEs will be assigned to the treatment phase, screening phase or follow-up phase as defined in Section [6.1](#).

An overall summary of AEs will be presented. This overall summary will comprise summary statistics for the class of other significant AEs according to ICH E3 and for the class of adverse events of special interest (AESI). For the definition of AESI please refer to Section 5.3.6.1 of the CTP.

The frequency of subjects with AEs will be summarised by treatment, primary system organ class and preferred term. AEs which were considered by the investigator to be drug related will be summarised separately. Separate tables will also be provided for subjects with serious AEs (SAEs), related SAEs, subjects with AESIs and subjects with other significant AEs (according to ICH E3 ([5](#))). AEs will also be summarized by maximum intensity.

The system organ classes will be sorted according to the standard sort order specified by the European Medicines Agency (EMA), preferred terms will be sorted by total frequency (within system organ class).

For disclosure of AE data on ClinicalTrials.gov, the frequency of subjects with non-serious AEs occurring with an incidence of greater than 5 % (in preferred terms) will be summarised by treatment, primary system organ class and preferred term. The frequency of subjects with SAEs will also be summarised.

For disclosure of AE data in the European union drug regulating authorities clinical trials (EudraCT) register, the frequency of AEs, the frequency of non-serious AEs with an incidence of greater than 5 % (in preferred terms) and the frequency of SAEs will be summarised.

